APPENDIX 2 EASTERN COOPERATIVE ONCOLOGY GROUP PERFORMANCE STATUS SCALE

Grade	Description
0	Fully active, able to carry on all pre-disease performance without restriction
1	Restricted in physically strenuous activity, but ambulatory and able to carry out work of a light or sedentary nature, e.g., light house work, office work
2	Ambulatory and capable of all self-care, but unable to carry out any work activities, up and about more than 50% of waking hours
3	Capable of only limited self-care, confined to bed or chair more than 50% of waking hours
4	Completely disabled. Cannot carry on any self-care. Totally confined to bed or chair
5	Dead

Table 9Eastern Cooperative Oncology Group Performance Status Scale

APPENDIX 3 NEW YORK HEART ASSOCIATION (NYHA) CLASSIFICATION

Class	Limitation on	Status at Rest	Symptoms with Ordinary Physical
	Physical Activity		Activity
Ι	None	Comfortable	Non
II	Slight	Comfortable	Symptomatic with greater than ordinary activities
III	Marked	Comfortable	Symptomatic with ordinary activities
IV	Unable to perform any activity	Symptomatic	Symptomatic at less than ordinary levels of activity

 Table 10
 New York Heart Association (NYHA) Classification

APPENDIX 4 CALCULATION OF THE CREATININE CLEARANCE

 $CrCl (male) = ([140-age] \times weight in kg)/(serum creatinine in mg/dL \times 72)$

CrCl (female) = CrCl (male) ×0.85

For SI units:

 $CrCl (male) = ([140-age] \times weight in kg)/(serum creatinine in \mu mol/L \times 1.23)$

 $CrCl (male) = ([140-age] \times weight in kg)/(serum creatinine in \mu mol/L \times 1.05)$

If the subject is obese (more than 30% of the ideal body weight), use the ideal weight to calculate CrCI

GFR (mL/min/1.73m²) = CrCl (mL/min)/(BSA \times 1.73)

Body Surface Area (BSA) (Dubois) = 0.007184 x (patient height in cm)^{0.725} ×(patient weight in kg)^{0.425} (two decimal place accuracy)

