	2. Subjects must have a histological diagnosis of locally advanced or metastatic malignant solid tumors. Subjects must have failed the established standard treatment, or the standard treatment does not exist; or subjects are intolerant of or have refused to receive standard treatment. All subjects must have received at least one previous line of systemic treatment. Subjects with known genomic alterations for which there are approved therapies (e.g., ALK mutated NSCLC, microsatellite instability high/mismatch repair deficient solid tumors, EGFR NSCLC, etc.,) will have received such therapies prior to the enrolling in this study.
	3. Subjects must have measurable or evaluable disease (according to RECIST 1.1, see Appendix 1);
	4. ECOG Performance Status ≤ 2 .
Inclusion Criteria	5. Life expectancy \geq 12 weeks.
	6. Subjects must have normal levels of total serum calcium and total phosphate.
	7. Subjects must have adequate organ and bone marrow function (subjects must not have received any hematopoietic growth factors, transfusion, or platelet within 1 week before the first dose).
	• CBC: neutrophils $\geq 1.5 \times 10^{9}$ /L, platelets $\geq 100 \times 10^{9}$ /L, hemoglobin ≥ 9.0 g/dL.
	• Liver function: total bilirubin $\leq 1.5 \times ULN$, unless known to have Gilbert's disease; ALT/AST $\leq 2.5 \times ULN$ without liver metastasis; ALT/AST $\leq 5 \times ULN$ with liver metastasis;
	• Coagulation: International normalized ratio (INR) $\leq 1.5 \times ULN$ and activated partial thromboplastin time (APTT) $\leq 1.5 \times ULN$ (for subjects undergoing anticoagulant therapy, the Investigator should ensure that both INR and APTT are within the safe and effective treatment range).

	 Renal function: serum creatinine ≤ 1.5 × ULN, or creatinine clearance ≥ 60 mL/min/1.73 m² in the condition of creatinine level > ULN; urine protein analysis ≤ 1 + (if ≥ 2+, 24 hours of urine protein test is required, if 24 hours urine protein <1 g, then allowed to enroll); Adequate cardiac function: left ventricular ejection fraction (LVEF) > 50% in two-dimensional echocardiography; 8. Subjects must have fully understood and voluntarily signed informed consent form (ICF) for this study.

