5.2. Inclusion Criteria

Subjects must meet all of the following criteria before they can be enrolled:

- 1. Age \geq 18 years.
- 2. Subjects must have a histological diagnosis of locally advanced or metastatic malignant solid tumors. Subjects must have failed the established standard treatment, or the standard treatment does not exist; or subjects are intolerant of or have refused to receive standard treatment. All subjects must have received at least one previous line of systemic treatment. Subjects with known genomic alterations for which there are approved therapies (e.g., ALK mutated NSCLC, microsatellite instability high/mismatch repair deficient solid tumors, EGFR NSCLC, etc.,) will have received such therapies prior to the enrolling in this study.
- 3. Subjects must have measurable or evaluable disease (according to RECIST 1.1, see Appendix 1);
- 4. ECOG Performance Status ≤ 2 .
- 5. Life expectancy ≥ 12 weeks.
- 6. Subjects must have normal levels of total serum calcium and total phosphate.
- 7. Subjects must have adequate organ and bone marrow function (subjects must not have received any hematopoietic growth factors, transfusion, or platelet within 1 week before the first dose).
 - CBC: neutrophils $\ge 1.5 \times 10^{9}$ /L, platelets $\ge 100 \times 10^{9}$ /L, hemoglobin ≥ 9.0 g/dL.
 - Liver function: total bilirubin $\leq 1.5 \times$ ULN, unless known to have Gilbert's disease; ALT/AST $\leq 2.5 \times$ ULN without liver metastasis; ALT/AST $\leq 5 \times$ ULN with liver metastasis;
 - Coagulation: $INR \le 1.5 \times ULN$ and $APTT \le 1.5 \times ULN$ (for subjects undergoing anticoagulant therapy, the Investigator should ensure that both INR and APTT are within the safe and effective treatment range).
 - Renal function: serum creatinine $\leq 1.5 \times \text{ULN}$, or creatinine clearance $\geq 60 \text{ mL/min}/1.73 \text{ m}^2$ in the condition of creatinine level > ULN; urine protein

analysis $\leq 1 + (\text{if } \geq 2+, 24 \text{ hours of urine protein test is required, if 24 hours urine protein <1 g, then allowed to enroll);$

- Adequate cardiac function: LVEF > 50% in two-dimensional echocardiography;
- 8. Subjects must have fully understood and voluntarily signed ICF for this study.

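### Appendix 4 miscalculates creatinine clearance: the BSA line is 2.99-fold too low, the SI constants divide instead of multiply, and the female SI line is labelled male

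*Protocol*

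**What the plan says.** Inclusion criterion 7 (Synopsis and Section 5.2) sets the renal requirement as "serum creatinine ≤ 1.5 × ULN, or creatinine clearance ≥ 60 mL/min/1.73 m² in the condition of creatinine level > ULN".

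Appendix 4, Calculation of the Creatinine Clearance, gives these lines:

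- Conventional units, men: "CrCl (male) = ([140-age] \times weight in kg)/(serum creatinine in mg/dL \times 72", with 72 inside the denominator.
- Women: "CrCl (female) = CrCl (male) ×0.85".
- SI units, first line: "CrCl (male) = ([140-age] \times weight in kg)/(serum creatinine in \mu mol/L \times 1.23", with 1.23 inside the denominator.
- SI units, second line: the same expression, again labelled male, ending in "serum creatinine in \mu mol/L \times 1.05".
- Normalisation: "GFR (mL/min/1.73m²) = CrCl (mL/min)/(BSA \times 1.73", with BSA × 1.73 inside the denominator.
- BSA by the Dubois formula to two decimals, and ideal weight in place of actual weight for obese subjects.

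The renal bullet of criterion 7 does not cite Appendix 4. No other calculation of creatinine clearance appears in the protocol, and the appendix ends in the same unit as the threshold.

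**The concern.** A subject whose BSA is exactly 1.73 m² should have the same clearance before and after normalisation. The printed line instead divides that subject's value by 2.99.

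The SI lines disagree with the mg/dL line of the same appendix, so one blood sample gives different clearances depending on the laboratory's reporting unit. With both SI lines labelled male, a man has two conflicting results and a woman has no SI line of her own.

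At stake is eligibility for subjects with creatinine above the ULN who depend on the clearance limb. All the errors push the value down, so a site that follows the appendix would turn away subjects who meet the criterion. A site using a standard calculator would not. In a study run in two countries, this means different entry rules at different sites.

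**Working it through.** **Inputs.** From Appendix 4: the constants 72, 0.85, 1.23, 1.05 and 1.73, and the Dubois formula. From criterion 7: the threshold of 60. Assumed, because the protocol does not give them: 1 mg/dL = 88.4 µmol/L (88.0 to 88.5 changes little), and the ULN values stated below.

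**1. BSA line.** Correct form: CrCl × 1.73/BSA. Printed form: CrCl/(BSA × 1.73). The ratio is 1.73 × 1.73 = 2.993, whatever the BSA, and needs no outside input. To show 60 as printed, the true normalised clearance must be 60 × 2.993 = 179.6.

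**2. Where the SI constants come from.** Write A = (140 − age) × weight and S = creatinine in µmol/L. The mg/dL line becomes A × 88.4/(72 × S) = 1.228 × A/S, so 1.23 is reproduced as a *multiplier*. Applying the appendix's female factor, 1.23 × 0.85 = 1.0455, which rounds to 1.05, also as a multiplier.

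**3. Check without the unit conversion.** The female-to-male ratio should be 0.85. As multipliers, 1.05/1.23 = 0.854. As printed divisors, the 1.05 line gives 1.23/1.05 = 1.171 times the 1.23 line, which is the wrong direction. The pair therefore fits the appendix only as male and female multipliers.

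**4. Size of the SI error.**

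| Printed line | Too low by | With the BSA error (× 2.993) |
|---|---|---|
| 1.23, men | 1.228 × 1.23 = 1.51 | 4.52 |
| 1.05, if meant for women | 0.85 × 1.228 × 1.05 = 1.10 | 3.28 |
| 1.05, if used for men as labelled | 1.228 × 1.05 = 1.29 | 3.86 |

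**5. Two worked subjects.**

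| | Man, 35 y, 80 kg, 175 cm, 1.6 mg/dL | Man, 45 y, 70 kg, 170 cm, 1.3 mg/dL |
|---|---|---|
| Position (assumed ULN) | above 1.5 × ULN (ULN 1.0) | between ULN and 1.5 × ULN (ULN 1.2) |
| BSA | 1.96 | 1.81 |
| CrCl, mg/dL line | 105 × 80/(1.6 × 72) = 72.9 | 95 × 70/(1.3 × 72) = 71.0 |
| Correct, CrCl × 1.73/BSA | 64.4 | 67.9 |
| Printed, CrCl/(BSA × 1.73) | 21.5 | 22.7 |
| CrCl, printed SI 1.23 line | 8400/(141.44 × 1.23) = 48.3 | 6650/(114.92 × 1.23) = 47.0 |
| Printed SI line, then printed BSA line | 14.2 | 15.0 |

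Both men reach 60 when calculated correctly and fall far below it as printed.

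**6. Can the printed formula reach 60 at all?** I scanned ages 18–90, heights 145–200 cm and BMI 17–35, with creatinine exactly at the ULN, the mg/dL line and actual weight. The highest printed value always falls at age 18, 200 cm and BMI 35:

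- Men: 50.2 at ULN 1.0, falling to 38.6 at ULN 1.3.
- Women: 53.4 at ULN 0.8, falling to 38.8 at ULN 1.1.

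None reaches 60. Creatinine above the ULN, or the SI lines, would lower these values further.

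**The case against.** The arithmetic is hard to dispute, so the case on the other side concerns consequence.

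- **The link to eligibility is inferred.** Criterion 7 does not cite Appendix 4, although other appendices are cited where they are used. The faulty line is labelled GFR, while the criterion speaks of creatinine clearance. Whether any site used the printed lines cannot be known. This stands, and the practical consequence is conditional on use of the appendix. It remains the only method offered, in the same unit as the only clearance threshold.
- **Few subjects may be affected.** Read literally, the word *or* lets anyone at or below 1.5 × ULN qualify on creatinine alone. Above that, the correct formula seldom reaches 60 either. On an unweighted grid (ages 50–75, heights 150–185 cm, BMI 19–30) with creatinine at 1.5 × ULN, about 3% of men reach 60 at ULN 1.0 and none at 1.1–1.3. About 10% of women do at ULN 0.8, and almost none at 0.9–1.1. This stands for the literal reading. The qualifier "in the condition of creatinine level > ULN" also permits a reading in which clearance is required for everyone above the ULN, and then practically all such subjects fail.
- **The first worked subject depends on the assumed ULN.** At ULN 1.2 he qualifies on creatinine alone, since 1.6 is below 1.8. At 1.81 mg/dL his correct value would be 56.9, a failure anyway. This is fair, but it limits the example and leaves the 2.99 factor intact.
- **The scan uses actual weight, whereas the appendix requires ideal weight in obesity.** With a conventional ideal-weight formula (an assumption) the maxima drop to about 46 for men and 47 for women. This strengthens the conclusion.
- **An operator may have been lost when the PDF was read.** This cannot be wholly excluded for the BSA line. Brackets and operators are intact, however, and no lost symbol explains the SI lines or the repeated label.

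**Conclusion.** The point holds. Three lines of Appendix 4 are wrong as written: the BSA normalisation, the first SI line (constant misplaced), and the second SI line (constant misplaced and sex mislabelled). The mg/dL line, the 0.85 factor and the Dubois formula are sound.

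The 2.99 factor rests on no assumption. The 1.10- to 1.51-fold SI errors rest on the 88.4 conversion, but their direction follows from the appendix's own 0.85. That the clearance limb is practically unattainable rests on sites using the appendix and on the ULN ranges scanned.

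The number of subjects affected runs from a few (those above 1.5 × ULN) to practically everyone above the ULN, depending on how criterion 7 is read. The error acts only at screening and only toward wrongful exclusion. It does not bear on the DLT rules, the choice of MTD or the sample size. It should be corrected, because a numeric entry threshold should not depend on a formula wrong by a factor of 3 to 4.5.

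**What to change.** Correct three lines of Appendix 4:

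1. Normalised clearance (mL/min/1.73 m²) = CrCl × 1.73/BSA.
2. SI units, male: CrCl = (140 − age) × weight × 1.23/creatinine in µmol/L.
3. SI units, relabelled female: CrCl = (140 − age) × weight × 1.05/creatinine in µmol/L.

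Leave the 60 mL/min/1.73 m² threshold as it is. Citing Appendix 4 in the renal bullet of criterion 7 would make the link explicit. Send sites a short memo and re-check any subject screened out on the clearance limb.

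The cost is close to nil: a three-line appendix correction, the memo, and a look through the screen failures.

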APPENDIX 5 PHOSPHORUS-RICH FOOD

Phosphorus is an important mineral element necessary for the human body. The main source of phosphorus in the human body is natural food or food phosphate additive. Phosphate is one of the most widely used and widely used food additive categories. As an important food ingredient and functional additive widely used in the processing of meat products, poultry products, seafood, fruits, vegetables, dairy products, bakery products, beverages, potato products, seasonings, convenience foods, etc.

The main source of phosphorus is diet. Therefore, controlling the intake of phosphorus in the diet is very important for the prevention and treatment of hyperphosphatemia^[21].

High phosphate-rich processed foods:

- Soft drinks, soda drinks, especially cola or carbonated and fizzy lemonade
- Cordials/fruit syrup beverages
- Chocolate, candy, and anything else with a high citric acid and sugar content
- Ice-cream
- Skim milk powder (often added to processed foods)
- Biscuits, cakes
- Tomato ketchup
- Mayonnaise
- Tahini
- Fish fingers
- Processed cheese, especially soft cheese spread
- Frozen pizzas
- Hot dogs
- Processed meats
- All foods that list as an ingredient mineral salts, emulsifiers and lecithin.

High phosphate-rich natural foods:

- Egg yolks
- Milk

- Nuts
- Wheat germ
- Soybeans and their by-products
- Peas
- Beans
- Lentils
- Kidney bean
- Pinto bean
- Corn
- Walnut
- Sunflower seed
- Peanuts
- Mushrooms
- Oats
- Cocoa beans (chocolate)
- Animal organs- liver, brains, kidne

APPENDIX 6 CYP3A4 STRONG INHIBITORS AND INDUCERS, AND CYP2C8 STRONG INHIBITORS

Table 11 CYP3A4 Strong Inhibitors and Inducers, and CYP2C8 Strong Inhibitors

CYP3A4 Strong Inhibitors	Nelfinavir, Indinavir, Voriconazol, Telithromycin, Ketoconazole, Nefazodone, Itraconazole, Clarithromycin, Saquinavir, Darunavir, Posaconazole, Lopinavir, Telaprevir, Boceprevir, Idelalisib, Cobicistat, Stiripentol, Curcumin, Ritonavir, Conivaptan, Troleandomycin, Mibefradil, Doxycycline, Efavirenz, Atazanavir, Tipranavir, Naloxone, Clotrimazole, Nilotinib, Laveridine, Loperamide, Ribociclib, Danoprevir, Elvitegravir, Midostaurin, Terfenadine, Ergotamine, Econazole
CYP3A4 Strong Inducers	Nevirapine, Rifampicin, Carbamazepine, Fosphenytoin, Pentobarbital, Phenobarbital, Phenytoin, Primidone, Rifapentine, Enzalutamide, Lumacaftor, St. John's Wort, Mitotane, Apalutamide, Quinine, Rimexolone, Rifaximin, Rifamycin, Topiramate, Oxcarbazepine, Midostaurin
CYP2C8 Strong Inhibitors	Gemfibrozil, Clopidogrel, Lopinavir, Fluvoxamine, Felodipine, Mometasone furoate, Zafirlukast, Sorafenib, Erlotinib, Dabrafenib, Troglitazone, Candesartan cilexetil, Salmeterol, Cholecalciferol, Trametinib, Fluticasone, Fluticasone furoate, Fluticasone propionate, Ritonavir

https://www.drugbank.ca/categories

Subject's other concomitant medications can be judged by reference to their instructions.

APPENDIX 7 i3+3 DESIGN ALGORITHM

Similar to the 3+3 design^[18], the i3+3 is rule-based design, and it is also an interval-based design similar to mTPI¹⁹ The dose-assignment recommendation of the i3+3 design is based on the current observed DLT occurence and the relative position of the toxicity probability equivalence interval (EI). For example, if the observed DLT occurence at the current dose is below the lower limit of the equivalence interval, the i3+3 dose-assignment recommendation will be escalation "E". The specific i3+3 algorithm is as follows:

Suppose dose 'd' is the dose currently used to treat patients, 'n' is the number of patients who have been treated at dose 'd', and 'x' is the number of patients who have experienced DLTs at dose 'd'. The i3+3 dose-assignment recommendation will depend on two quantities x/n and (x-1)/n.

• If x/n is below the EI, escalate (E) and enroll patients at the next higher dose (d+1);

• If x/n is inside the EI, stay (S) and continue to enroll patients at the current dose d;

- If x/n is above the EI, there are two scenarios,
 - If (x-1)/n is below the EI, stay (S) and continue to enroll patients at the current dose d;
 - Else, de-escalate (D) and enroll patients at the next lower dose (d-1)

According to the above i3+3 algorithm and the preset EI, the i3+3 dose-assignment recommendation can be summarized in a decision table (Figure 1).

APPENDIX 8 SIMULATION TEST FOR i3+3 AND 3+3 DESIGNS

Simulation setup

[figure not shown]
We conducted a simulation trial using U-Design v1.1.5 (udesign.laiyaconsulting.com). The statistical performance of the i3+3 and 3+3 (Storer, 1989) designs was compared according to the study setup of the 3D185 phase 1 clinical trial in China. In this study, there are 7 escalating dose levels will be evaluated, the first two dose levels will use accelerated titration dose-escalation design, and the remaining five dose levels will use i3+3 dose escalation design. If a Grade ≥ 2 drug-related AE occurs during the accelerated titration phase, the current dose level will become the initial dose level in the i3+3 phase. Therefore, the initial dose of the i3+3 may have three different conditions: 100 mg (Cohort 3), 50 mg (Cohort 2), or 25 mg (Cohort 1). And the maximum sample size in each condition will be 30, 36, and 42, respectively. Each cohort will enroll 3 subjects. The MTD target toxicity probability pT = 25%, the choice of $\varepsilon 1$ is 0.09, and the choice of $\varepsilon 2$ is 0.05, so the EI is (16%, 30%). We simulated six different scenarios (Table 12) and three different starting dose settings, and performed 1,000 simulations for each of the "Scenario* Starting Dose".

Scenarios	рТ (%)	Times	True Toxicity Probability of Each Dose						
Scenarios	p1 (70)	Times	Dose 1	Dose 2	Dose 3	Dose 4	Dose 5	Dose 6	Dose 7
1	0.25	1000	0.1	0.25	0.35	0.45	0.55	0.65	0.75
2	0.25	1000	0.04	0.08	0.13	0.2	0.25	0.35	0.5
3	0.25	1000	0.04	0.08	0.12	0.16	0.2	0.24	0.28
4	0.25	1000	0.38	0.43	0.48	0.53	0.58	0.63	0.68
5	0.25	1000	0.04	0.08	0.12	0.16	0.45	0.55	0.65
6	0.25	1000	0.05	0.1	0.42	0.49	0.57	0.64	0.7

Simulation results (i3+3 vs 3+3)

The simulation results of the six scenarios were summarized in Figure 2-4 and Table 13-14. Figure 2 and Table 13 summarized the simulation results for the initial dose of Dose 3. Figure 3 and Table 14 summarized the simulation results for the initial dose of Dose 2. Figure 4 and Table 15 summarized the simulation results for the initial dose of Dose 1. For example, in Table 13, each scenario included two sub-tables. The upper sub-table contained 4 parts. The first part listed the target toxicity probability pT, the dose level, and true toxicity probabilities. The next three parts listed the selection probability, number of subjects treated, and the number of toxicities. The lower sub-table summarized four indicators that reflect the safety and reliability of the study, including the probability of selecting the true MTD, the probability of toxicity (proportion of subjects who have experienced DLT), the probability of select dose over-MTD, and the probability of no selection. Figure 2 showed these four indicators for all scenarios and all design methods in Table 13 by line graph.

[figure not shown]
Figure 2-4 and Table 13-14 showed that the i3+3 design has superior operating characteristics compared to the traditional 3+3 design. For example, in most scenarios, i3+3 has a higher probability of select true MTD, while having a smaller probability of select dose over-MTD.

* Mean ± Standard deviation. The statistics are calculated given by the current scenario and design setting.

Figure 2 Comparison of the i3+3 design with the 3+3 design (starting at Dose 3).

[figure not shown]
Design 1 was an i3+3 design with a maximum sample size of 30 (blue line) and design 2 was a 3+3 design (red line). The mean ±standard deviation of the statistical indicators for all simulation scenarios was summarized below the line graph. The probability of select true MTD was the percentage of trials that correctly select the true MTD in all 1000 simulation trials. The higher the value, the better the reliability of the design. The probability of toxicity was the percentage of subjects who developed DLT in all the 1000 simulated trials, and the lower the number, the better the safety of the design. The probability of select dose over-MTD in all the 1000 simulated trials, the study design selected a dose higher than the true MTD as the percentage of the MTD. The lower the value, the better the safety of the design. The probability of not selecting any dose indicates that in all the 1000 simulated trials, no dose was selected as the percentage of the MTD. If this scenario does not exist real MTD, the higher value the better.

* Mean ± Standard deviation. The statistics are calculated given by the current scenario and design setting.

Figure 3 Comparison of the i3+3 design with the 3+3 design (starting at Dose 2).

Design 1 was an i3+3 design with a maximum sample size of 36 (blue line) and design 2 was a 3+3 design (red line). The mean ±standard deviation of the stati stical indicators for all simulation scenarios was summarized below the line graph. The probability of select true MTD was the percentage of trials that correctly select the true MTD in all 1000 simulation trials. The higher the value, the better the reliability of the design. The probability of toxicity was the percentage of subjects who developed DLT in all the 1000 simulated trials, and the lower the number, the better the safety of the design. The probability of select dose over-MTD in all the 1000 simulated trials, the study design selected a dose higher than the true MTD as the percentage of the MTD. The lower the value, the better the safety of the design. The probability of not selecting any dose indicates that in all the 1000 simulated trials, no dose was selected as the percentage of the MTD. If this scenario does not exist real MTD, the higher value the better.

* Mean ± Standard deviation. The statistics are calculated given by the current scenario and design setting.

Figure 4 Comparison of the i3+3 design with the 3+3 design (starting at Dose 1).

Design 1 was an i3+3 design with a maximum sample size of 42 (blue line) and design 2 was a 3+3 design (red line). The mean ±standard deviation of the statistical indicators for all simulation scenarios was summarized below the line graph. The probability of select true MTD was the percentage of trials that correctly select the true MTD in all 1000 simulation trials. The higher the value, the better the reliability of the design. The probability of toxicity was the percentage of subjects who developed DLT in all the 1000 simulated trials, and the lower the number, the better the safety of the design. The probability of select dose over-MTD in all the 1000 simulated trials, the study design selected a dose higher than the true MTD as the percentage of the MTD. The lower the value, the better the safety of the design. The probability of not selecting any dose indicates that in all the 1000 simulated trials, no dose was selected as the percentage of the MTD. If this scenario does not exist real MTD, the higher value the better.

Table 13Comparison of i3+3 and 3 + 3 designs (starting at Dose 3 [100 mg])

The i3+3 design was marked in blue with a maximum sample size of 30 and a 3+3 design marked in red. The orange line represented the dose of the true MTD. A dose level without an orange marker indicated that this dose was not a true MTD and should not be selected as the MTD.

	Scenario 1											
		Selectio	n Prob.	# of Subjec	ts Treated	# of To	xicities					
Dose Level	True Tox Prob.	i3+3	3+3	i3+3	3+3	i3+3	3+3					
1	0.10	0.31	0.29	4.329	1.926	0.441	0.201					
2	0.25	0.42	0.348	10.827	3.714	2.665	0.959					
3	0.35	0.201	0.266	11.733	5.043	4.069	1.775					
4	0.45	0.019	0.054	2.691	1.863	1.235	0.856					
5	0.55	0.001	0.005	0.375	0.396	0.209	0.228					
6	0.65	0	0	0.027	0.033	0.018	0.018					
7	0.75	0	0	0	0.006	0	0.002					
			i3+3			3+3	-					
Prob. of S	Select MTD		0.42		0.348							
Prob. of Toxicity		0.288			0.311							
Prob. of Select Dose- over-MTD			0.221			0.325						

	o. of No ection		0.049		0.037			
			S	cenario 2				
		Selectio	n Prob.	# of Subjec	cts Treated	# of To	xicities	
Dose Level	True Tox Prob.	i3+3	3+3	i3+3	3+3	i3+3	3+3	
1	0.04	0.004	0.014	0.084	0.084	0.004	0.006	
2	0.08	0.043	0.144	1.587	0.936	0.128	0.08	
3	0.13	0.274	0.285	10.002	4.572	1.335	0.607	
4	0.20	0.353	0.229	9.576	4.059	1.925	0.855	
5	0.25	0.255	0.217	5.91	3.012	1.461	0.743	
6	0.35	0.064	0.089	2.343	1.803	0.824	0.659	
7	0.5	0.003	0.022	0.48	0.531	0.252	0.282	
			i3+3			3+3	1	
Prob. of	Select MTD		0.608		0.446			
Prob. o	f Toxicity		0.198		0.216			
Prob. of Select Dose- over-MTD		0.067			0.111			
Prob. of No Selection		0.004			0			

	Scenario 3											
		Selectio	n Prob.	# of Subjec	cts Treated	# of To	oxicities					
Dose Level	True Tox Prob.	i3+3	3+3	i3+3	3+3	i3+3	3+3					
1	0.04	0.002	0.008	0.057	0.048	0	0.002					
2	0.08	0.03	0.131	1.176	0.834	0.077	0.066					
3	0.12	0.18	0.199	8.895	4.347	1.089	0.537					
4	0.16	0.283	0.196	8.52	3.975	1.366	0.651					
5	0.20	0.258	0.178	6.039	3.204	1.204	0.656					
6	0.24	0.158	0.143	3.276	2.325	0.76	0.535					
7	0.28	0.089	0.145	2.037	1.287	0.575	0.397					
			i3+3			3+3						
Prob. of	Select MTD		0.788			0.662						
Prob. o	of Toxicity	0.169			0.178							
	Select Dose- r-MTD	0			0							
Prob. of No Selection		0										
			S	cenario 4								
		Selectio	on Prob.	# of Subje	cts Treated	# of To	oxicities					

Dose Level	True Tox Prob.	i3+3	3+3	i3+3	3+3	i3+3	3+3	
1	0.38	0.251	0.164	12.045	3.423	4.546	1.354	
2	0.43	0.06	0.177	7.122	4.137	3.062	1.769	
3	0.48	0.021	0.119	6.327	4.563	3.06	2.187	
4	0.53	0.003	0.01	0.924	0.873	0.468	0.469	
5	0.58	0	0.003	0.108	0.099	0.07	0.058	
6	0.63	0	0	0.006	0.021	0.003	0.009	
7	0.68	0	0	0	0.006	0	0.002	
			i3+3		3+3			
Prob. of S	Select MTD		0.665		0.527			
Prob. of	f Toxicity		0.422			0.446		
	elect Dose- [.] -MTD		0.335			0.473		
	. of No ection		0.665			0.527		
			S	cenario 5				
	Selection Prob. # of Subje			# of Subje	cts Treated	# of To	oxicities	
Dose Level	True Tox Prob.	i3+3	3+3	i3+3	3+3	i3+3	3+3	
1	0.04	0.002	0.007	0.057	0.042	0	0.003	

Dose Level	True Tox Prob.	i3+3	3+3	i3+3	3+3	i3+3	3+3			
		Selection Prob. # of Subjects Treated # of Toxici								
Scenario 6										
Sele	ection		0.001			0				
Prob	. of No		0.001							
	elect Dose- [.] -MTD		0.071		0.107					
Prob. of	f Toxicity		0.218			0.233				
Prob. of S	Select MTD	0.702			0.527					
			i3+3	1	3+3					
7	0.65	0	0.001	0.06	0.072	0.046	0.048			
6	0.55	0.004	0.008	0.702	0.708	0.361	0.394			
5	0.45	0.067	0.098	6.609	3.135	2.982	1.401			
4	0.16	0.702	0.527	12.36	4.806	1.971	0.813			
3	0.12	0.194	0.229	9.033	4.365	1.106	0.519			
2	0.08	0.03	0.13	1.179	0.822	0.077	0.073			

0.05

0.10

0.42

0.025

0.849

0.106

0.101

0.685

0.177

1

2

3

20191118

0.765

12.828

14.844

0.618

4.65

4.779

0.038

1.288

6.19

0.026

0.514

2.017

0.49	0.006	0.033	1.422	1.299	0.724	0.637	
0.57	0	0.001	0.132	0.225	0.076	0.132	
0.64	0	0.001	0.009	0.012	0.006	0.007	
0.70	0	0	0	0.003	0	0.002	
		i3+3		3+3			
lect MTD		0.849		0.685			
ſoxicity	0.277			0.288			
Prob. of Select Dose- over-MTD		0.112			0.212		
Prob. of No Selection		0.014			0.002		
	0.57 0.64 0.70 lect MTD Coxicity ect Dose- MTD	0.57 0 0.64 0 0.70 0 0.70 0 Ilect MTD	0.57 0 0.001 0.64 0 0.001 0.70 0 0 0.70 0 0 0.70 0 0 0.70 0 0 0.70 0 0 0.70 0 0 0.70 0 0 0.70 0 0 0.70 0 0 0.70 0 0 0.849 0.277 ect Dose- MTD 0.112 0f No 0.014	0.57 0 0.001 0.132 0.64 0 0.001 0.009 0.70 0 0 0 0.70 0 0 0 i3+3 0.849 0.277 coxicity 0.277 0.112 of No 0.014 0.014	0.57 0 0.001 0.132 0.225 0.64 0 0.001 0.009 0.012 0.70 0 0 0 0.003 0.70 0 0 0 0.003 lect MTD 0.849	0.57 0 0.001 0.132 0.225 0.076 0.64 0 0.001 0.009 0.012 0.006 0.70 0 0 0 0 0.003 0 0.70 0 0 0 0 0.003 0 0.70 0 0 0 0 0.003 0 0.70 0 0 0 0 0.003 0 0.70 0 0 0 0 0.003 0 0.70 0 0 0 0 0.003 0 0.70 0 0 0 0 0.003 0 0.70 0.849 0.685 0.288 0.288 0.212 of No 0.014 0.012 0.021	

Table 14Comparison of i3+3 and 3 + 3 designs (starting at Dose 2 [50 mg])

The i3+3 design was marked in blue with a maximum sample size of 36 and a 3+3 design marked in red. The orange line represented the dose of the true MTD. A dose level without an orange marker indicated that this dose was not a true MTD and should not be selected as the MTD.

	Scenario 1												
		Selectio	n Prob.	# of Subjec	ts Treated	# of To	xicities						
Dose Level	True Tox Prob.	i3+3	3+3	i3+3	3+3	i3+3	3+3						
1	0.10	0.333	0.389	7.677	2.679	0.766	0.298						
2	0.25	0.516	0.363	19.479	5.151	4.853	1.26						

3	0.35	0.117	0.141	7.23	2.967	2.533	1.098		
4	0.45	0.008	0.042	1.404	1.068	0.638	0.479		
5	0.55	0	0.003	0.171	0.27	0.092	0.151		
6	0.65	0	0	0.003	0.015	0.002	0.01		
7	0.75	0	0	0	0	0	0		
			i3+3			3+3			
Prob. of	Select MTD		0.516			0.363			
Prob. o	f Toxicity		0.247			0.271			
	of Select over-MTD		0.125		0.186				
	o. of No ection	0.026				0.062			
			S	cenario 2	1				
		Selectio	on Prob.	# of Subjects Treated # of Toxicitie			xicities		
Dose Level	True Tox Prob.	i3+3	3+3	i3+3	3+3	i3+3	3+3		
1	0.04	0.002	0.074	0.366	0.456	0.016	0.024		
2	0.08	0.057	0.057 0.15 6.999		3.999	0.573	0.342		
3	0.13	0.254	0.254 0.236 10.128		4.197	1.353	0.546		
4	0.20	0.363	0.208	9.732	3.765	1.925	0.776		

6	0.35	0.068	0.078	2.268	1.74	0.801	0.647
7	0.5	0.005	0.019	0.531	0.474	0.259	0.244
			i3+3	1		3+3	1
Prob. of S	Select MTD		0.614			0.441	
Prob. of	f Toxicity		0.179			0.185	
	of Select ver-MTD		0.073			0.097	
	o. of No ection		0		0.002		
			S	cenario 3	1		
		Selectio	on Prob.	# of Subjects Treated # of Toxic			oxicities
Dose Level	True Tox Prob.	i3+3	3+3	i3+3	3+3	i3+3	3+3
1	0.04	0.002	0.061	0.36	0.378	0.016	0.017
2	0.08	0.041	0.141	6.621	3.987	0.54	0.319
3	0.12	0.174	0.164	8.811	4.014	1.055	0.513
4	0.16	0.301	0.191	8.691	3.651	1.396	0.579
5	0.20	0.246	0.182	5.979	3.024	1.221	0.611
6	0.24	0.141	0.114	3.462	2.223	0.846	0.566
7	0.28	0.095	0.145	2.076	1.134 0.577 0.323		
			i3+3			3+3	

Prob. of Select MTD Prob. of Toxicity			0.783			0.632			
		0.157			0.159				
	of Select ver-MTD		0			0			
	o. of No ection		0			0.002			
			Sce	enario 4	 				
		Selectio	on Prob.	# of Subjec	ts Treated	# of To	oxicities		
Dose Level	True Tox Prob.	i3+3	i3+3 3+3 i3·		3+3	i3+3	3+3		
1	0.38	0.187	0.193	17.322	3.927	6.532	1.523		
2	0.43	0.035	0.181	8.214	4.749	3.517	2.021		
3	0.48	0.001	0.03	1.512	1.242	0.751	0.629		
4	0.53	0	0.001	0.186	0.222	0.099	0.119		
5	0.58	0	0	0.012	0.024	0.007	0.012		
6	0.63	0	0.001	0	0.006	0	0.001		
7	0.68	0	0	0	0.003	0	0.002		
		i3+3		1		3+3			
Prob. of Select MTD		0.777			0.594				
Prob. of Toxicity		0.4			0.423				
Prob. of Select Dose-over-MTD			0.223			0.406			

	o. of No ection	0.777 0.594						
			S	Scenario 5				
		Selectio	n Prob.	# of Subjec	ets Treated	# of To	oxicities	
Dose Level	True Tox Prob.	i3+3	3+3	i3+3	3+3	i3+3	3+3	
1	0.04	0.002	0.058	0.36	0.354	0.016	0.018	
2	0.08	0.042	0.145	6.633	3.987	0.541	0.315	
3	0.12	0.183	0.194	8.985	4.089	1.083	0.511	
4	0.16	0.715	0.51	12.666	4.398	2.051	0.744	
5	0.45	0.055	0.082	6.753	2.955	3.082	1.359	
6	0.55	0.003	0.01	0.549	0.609	0.307	0.349	
7	0.65	0	0	0.054	0.078	0.029	0.05	
			i3+3			3+3		
Prob. of	Select MTD		0.715			0.51		
Prob. o	f Toxicity		0.197		0.203			
	of Select over-MTD		0.058		0.092			
Prob. of No Selection		0			0.001			
			S	cenario 6				
		Selectio	n Prob.	# of Subjec	ets Treated	# of To	xicities	

Dose Level	True Tox Prob.	i3+3	3+3	i3+3	3+3	i3+3	3+3		
1	0.05	0.009	0.111	0.816	0.678	0.039	0.031		
2	0.10	0.885	0.698	18.192	5.466	1.865	0.567		
3	0.42	0.1	0.154	15.366	4.176	6.463	1.8		
4	0.49	0.005	0.032	1.467	1.14	0.739	0.544		
5	0.57	0	0.002	0.153	0.198	0.087	0.112		
6	0.64	0	0.001	0.006	0.033	0.005	0.017		
7	0.70	0	0	0	0.003	0	0.002		
			i3+3		3+3				
Prob. of S	Select MTD		0.885			0.698			
Prob. o	f Toxicity		0.256 0.263						
	Prob. of Select 0.105 0.1			0.105					
	o. of No ection		0.001			0.002			

Table 15Comparison of i3+3 and 3 + 3 designs (starting at Dose 1 [25 mg])

The i3+3 design was marked in blue with a maximum sample size of 42 and a 3+3 design marked in red. The orange line represented the dose of the true MTD. A dose level without an orange marker indicated that this dose was not a true MTD and should not be selected as the MTD.

		Selectio	on Prob.	# of Subjec	ts Treated	# of To	oxicities
Dose Level	True Tox Prob.	i3+3	3+3	i3+3	3+3	i3+3	3+3
1	0.1	0.34	0.42	13.764	4.782	1.353	0.493
2	0.25	0.536	0.314	19.29	4.569	4.779	1.17
3	0.35	0.106	0.125	7.02	2.571	2.452	0.928
4	0.45	0.015	0.035	1.623	0.933	0.71	0.425
5	0.55	0	0.003	0.183	0.228	0.1	0.127
6	0.65	0	0	0.012	0.018	0.007	0.012
7	0.75	0	0	0	0	0	0
			i3+3	1		3+3	
Prob. of S	Select MTD		0.536			0.314	
Prob. of	f Toxicity		0.224			0.241	
	of Select ver-MTD	0.121			0.163		
	o. of No ection		0.003			0.103	
			S	Scenario 2			
		Selectio	on Prob.	# of Subjec	ts Treated	# of To	xicities
Dose Level	True Tox Prob.	i3+3	3+3	i3+3	3+3	i3+3	3+3
1	0.04	0.002	0.061	4.434	3.456	0.197	0.129

2	0.08	0.05	0.152	6.588	3.957	0.5	0.321	
	0.08	0.03	0.132	0.388	3.937	0.3	0.321	
3	0.13	0.267	0.222	11.106	4.143	1.495	0.567	
4	0.2	0.363	0.233	10.431	3.672	2.109	0.707	
5	0.25	0.246	0.217	6.204	2.916	1.552	0.734	
6	0.35	0.071	0.077	2.835	1.59	1.011	0.611	
7	0.5	0.001	0.019	0.402	0.495	0.201	0.25	
			i3+3	1		3+3		
Prob. of S	Select MTD		0.609			0.45		
Prob. o	f Toxicity		0.168			0.164		
	of Select ver-MTD	0.072				0.096		
	o. of No ection		0			0.019		
			Sce	enario 3	1			
		Selectio	n Prob.	# of Subjec	ts Treated	# of To	xicities	
Dose Level	True Tox Prob.	i3+3	3+3	i3+3	3+3	i3+3	3+3	
1	0.04	0.002	0.002 0.064 4.422 3.52			0.194	0.149	
2	0.08	0.038	0.132	6.327	3.906 0.487 0.32			
3	0.12	0.176	0.155	9.408	3.909	1.171	0.495	
4	0.16	0.272	0.191	8.823	3.585	1.419	0.562	

5	0.2	0.252	0.183	6.447	3.099	1.256	0.626	
6	0.24	0.163	0.101	4.017	2.118	0.97	0.534	
7	0.28	0.097	0.154	2.556	1.17	0.701	0.311	
			i3+3			3+3		
Prob. of S	Select MTD		0.784			0.629		
Prob. o	f Toxicity		0.148			0.141		
	of Select ver-MTD		0			0		
	o. of No ection	0			0.02			
			S	cenario 4				
		Selectio	n Prob.	# of Subjec	ts Treated # of Toxicities			
Dose Level	True Tox Prob.	i3+3	3+3	i3+3	3+3	i3+3	3+3	
1	0.38	0.149	0.218	22.062	4.908	8.333	1.831	
2	0.43	0.007	0.047	2.409	1.641	1.038	0.736	
3	0.48	0	0.015	0.372	0.426	0.183	0.201	
4	0.53	0	0	0.045	0.096 0.025 0.05			
5	0.58	0	0.001	0	0.012	0	0.006	
6	0.63	0	0	0	0.003	0	0.002	
7	0.68	0	0	0	0	0	0	

			i3+3			3+3			
Prob. of	Prob. of Select MTD		0.844			0.719			
Prob. o	f Toxicity		0.385			0.399			
	of Select over-MTD		0.156			0.281			
	o. of No ection		0.844			0.719			
			S	Scenario 5	1				
		Selectio	on Prob.	# of Subjec	bjects Treated # of Toxic		xicities		
Dose Level	True Tox Prob.	i3+3	3+3	i3+3	3+3	i3+3	3+3		
1	0.04	0.002	0.056	4.422	3.48	0.194	0.143		
2	0.08	0.038	0.128	6.327	3.951	0.487	0.324		
3	0.12	0.188	0.199	9.588	4.071	1.188	0.509		
4	0.16	0.705	0.491	13.497	4.395	2.161	0.731		
5	0.45	0.065	0.102	7.389	2.988	3.306	1.34		
6	0.55	0.002	0.009	0.726	0.642	0.38	0.367		
7	0.65	0	0.001	0.051	0.063	0.038	0.04		
			i3+3			3+3	I		
Prob. of	Prob. of Select MTD		0.705		0.491				
Prob. of Toxicity		0.185				0.176			

Prob. of Select Dose-over-MTD		0.067			0.112			
	o. of No ection		0			0.014		
			Sce	enario 6				
		Selectio	on Prob.	# of Subjec	ts Treated	# of To	oxicities	
Dose Level	True Tox Prob.	i3+3	i3+3 3+3		3+3	i3+3	3+3	
1	0.05	0.005	0.126	5.127	3.741	0.283	0.178	
2	0.1	0.883	0.677	18.99	5.4	1.872	0.572	
3	0.42	0.105	0.151	16.335	4.155	6.847	1.753	
4	0.49	0.007	0.022	1.413	1.029	0.694	0.524	
5	0.57	0	0.002	0.129	0.171	0.074	0.099	
6	0.64	0	0	0.006	0.024	0.004	0.011	
7	0.7	0	0	0	0	0	0	
			i3+3	1		3+3		
Prob. of	Select MTD		0.883		0.677			
Prob. of Toxicity 0.233 0		0.216						
Prob. of Select Dose-over-MTD		0.112			0.175			
	o. of No ection		0			0.022
